	
SSE(s): Self-skin-exam(s) performed by Participants at-home
 
FBSE(s): Full body skin exam(s) performed by DPs in-office
 
SCI-TD: Expert dermatologist consensus SCI triage decision
 
DDI-GT: Expert dermatologist consensus DDI dermoscopic diagnosis
 
DHI: Digital histologic image of a target PSLC biopsied during the In-person Phase
 
EMR: Electronic medical record

Study Device Hardware	The Sklip dermatoscope device hardware will be provided to Participants to take DDI of their self-selected PSLCs using their smartphone or tablet. The Sklip dermatoscope is publicly (commercially) available and registered as a Class 1 Medical Device (FDA Reg. 3017732705).
Study Site Secure Smartphone and Sklip	The sponsor will provide one (1) smartphone to each Study Site, one (1) unique passcode access to the SMSA within the Sklip App, one (1) Sklip dermatoscope (with charging cable, instructions, and dermoscopy oil) for use with Participants in-office. Clear instructions will be given to delete all images from the native smartphone photo App gallery after Study Site Coordinators upload required data and images to the OHSU secure cloud, prior to returning the smartphone to the Sponsor. This will ensure no patient health information leaves the Study Site on physical hardware.
Study App	The Sklip App is a publicly available smartphone App to download on the Apple iOS and Google Play app stores. The Sklip App is non-FDA regulated and part of the approved protocol for the Melanoma Community Registry (OHSU IRB# 10561). A security review of the Sklip App has been performed as part of that Study and is transferred to this Study protocol.
Sklip Mole Scan Algorithm (SMSA)	The proprietary SMSA sensitivity triage performance is: 97.4% for melanoma and atypical melanocytic nevi with uncertain malignant potential, 97.0% for squamous cell carcinoma, 97.3% for basal cell carcinoma.

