Potential solution: Sklip System may help reduce layperson concerns about benign skin lesions due to safe and accurate triage based on pre-specified performance goals by the FDA. This may allow DPs to have more confidence not seeing the patient in person for an otherwise benign concern and improve access for patients with actual malignancies that may be detected by the SMSA. Additionally, in the case of SMSA SUSPICIOUS output, the user is clearly prompted to urgently contact a healthcare Provider.

e) **Reduced access and delay of care** due to increased wait times to see DPs in-office.

Potential solution: Sklip System would be used by laypersons as a stand-alone device to triage PSLCs. This could potentially improve access for persons with verified SUSPICIOUS PSLCs that require immediate in-person evaluation by a DP. FDA Clearance of the Sklip System could potentially streamline the time to treat for persons with skin malignancies who are currently delayed by the current medical system triage status quo.

The Sklip System has been reviewed by the FDA and received “Breakthrough Designation Status” with a reported overall sensitivity of 94.47% and specificity of 83.33%, compared to the highest reported accuracy by primary care providers using dermoscopy – sensitivity of 79.2% and specificity of 72.5%. The current SMSA Performance reported sensitivity for melanoma and atypical melanocytic nevi with uncertain malignant potential is 97.4% (2023).

Of note, an estimated fifty (50) percent of PSLC biopsies occur in primary care settings. The functionality of DDI based triage using Sklip System by laypersons, that is the same, or superior, to an in-person spot check visit with a primary care Provider for a layperson self-selected PSLC, could have a significant impact on streamlining and improving the safety of current patient care access. This should be evaluated in a research setting.

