#### Device Description

The **Sklip dermatoscope** device hardware will be provided to Participants to take DDI of their self-selected PSLCs using their smartphone or tablet. The Sklip dermatoscope is publicly (commercially) available and registered as a Class 1 Medical Device (FDA Reg. 3017732705).

The **Sklip App** is a publicly available smartphone App to download on the Apple iOS and Google Play app stores. The Sklip App is non-FDA regulated and part of the approved protocol for the Melanoma Community Registry (OHSU IRB# 10561). A security review of the Sklip App has been performed as part of that Study and is transferred to this Study protocol.

The proprietary **SMSA** evaluation of DDI has a reported Melanoma and atypical melanocytic nevi with uncertain malignant potential sensitivity Performance of 97.4% (2023).

The **Sklip System** is a SaMD that received breakthrough designation by the FDA on June 22, 2021. The Sklip System is intended to record, store and transfer DDI. The Sklip System consists of the Sklip App (used on a smartphone or tablet) and SMSA, that accept DDI taken by dermatoscope hardware. The Sklip System also displays DDI and non-diagnostic output of DDI analysis from the Sklip System software library that implements various DDI processing and artificial intelligence (Ai) analysis. This SaMD computes various digital parameters from DDI and provides these capabilities in the form of an API library. DDI can be incorporated into the Sklip System software to enable algorithmic analysis and analytics of DDI by the SMSA. The SMSA, is a software workflow tool designed to aid the assessment of DDI data input intended to conduct an initial screening of DDI for features suggestive of skin cancer and flag suspicious DDI for expedited review by appropriate medical personnel, such as a dermatology Provider (Dermatologist or dermatology trained APP), or primary care Provider (PCP). Specifically, the SMSA, via the Sklip System " Scan Moles with Ai" function, uses a Sklip Inc. proprietary Ai algorithm to provide DDI filtering, detection of noisy (non-qualified) DDI and detection of skin lesions containing qualified pigment that may be remarkable for MD3PC features ((DRFs): dermoscopic asymmetry, dermoscopic round structures and/or dermoscopic blue-white colors), which may be indicative of skin cancer.

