#### 11.2 SAMPLE SIZE DETERMINATION

Sample size was calculated using formulas based on normal approximation to the binomial distribution. Previously recorded historical biopsy results for Melanoma, Squamous cell carcinoma, and Basal cell carcinoma across the proposed Study Sites averaged 2.3%, 12.5% and 29.2% of in-person dermatology Provider visits (i.e. cases), respectively. This represents disease prevalence rates in this pivotal Study target population of interest (i.e. patients who visited a Study Site within a 365 day period specifically for a mole spot check with concern for skin cancer, or a full body skin exam (FBSE) for the purpose of skin cancer prevention. This calculation presumes the exclusion of all other dermatology visits not related to a concern for skin cancer. Formulae (1) and (2) were used to estimate the sample size needed to evaluate the sensitivity (Se) and specificity (Sp), based on the diagnostic performance data available for melanoma from the SMSA Performance Study, and the target population case prevalence rates. The following values are inserted:  $Z_{\alpha/2} = 1.96$  for  $\alpha = 0.05$  level of significance, and  $d = 10\%$  margin of error for 95% Confidence Interval.

$$n_{Se} = \frac{Z_{\frac{\alpha}{2}}^2 \widehat{Se} (1 - \widehat{Se})}{d^2 \times \text{Prev}} \quad (1)$$

$$n_{Sp} = \frac{Z_{\frac{\alpha}{2}}^2 \widehat{Sp} (1 - \widehat{Sp})}{d^2 \times (1 - \text{Prev})} \quad (2)$$

Table 4 and Table 5 below summarizes the sample size estimates for cutaneous diseases of interest to evaluate the sensitivity and specificity of the investigational device (Sklip System). As can be seen from the table, the size estimate calculated using the sensitivity value for detecting melanoma (423 cases [lesions]) yields the largest number. The expected numbers of lesions that will be accordingly captured during the Study are summarized in Table 6.

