Considering the larger number of cases required for evaluation of sensitivity (423 for Melanoma; based on SMSA performance of sensitivity for melanoma of 97.4%) as opposed to specificity (114 for SCC), a 49% specificity can be estimated from the hypothetical sample data. Previous peer-reviewed studies, exclusive to virtual visits, showed that participants submitted an average of 1.02 to 1.9 images per participant. Considering the aforementioned and average case submission rates reported by the proposed Study Sites, we expect a case submission rate of 1.5 per Study Participant. Assuming a 10% drop-out rate a total number of 310 Participants (dropout-inflated sample size) will be needed for the current study (310 = 423 ÷ 1.5 × 1.10).

**Table 4. Sample size estimates for cutaneous diseases of interest to evaluate the sensitivity of Sklip System based on the available target population prevalence data.**

Lesions	Sample Size Estimate to Test for Sensitivity											
	Melanoma			BCC			SCC			AMN		
	Confirmed	Excluded	Total	Confirmed	Excluded	Total	Confirmed	Excluded	Total	Confirmed	Excluded	Total
Suspicious	9	248	257	17	89	107	17	31	48	17	243	260
Non-Suspicious	1	165	166	1	38	39	1	13	14	1	104	105
Total Scanned	10	413	423	18	128	146	18	44	63	18	347	365
Prevalence	2.3%			12.5%			29.2%			5.0%		
Sensitivity	97.4%			95%			95%			95%		
Specificity	40%			30%			30%			30%		

The sample size was estimated using formulae (1) and (2) to test for sensitivity and specificity, respectively, with  $\alpha = 0.05$  significance level and 10% margin of error for 95% Confidence Interval. The respective sensitivity and specificity values were used to estimate the numbers of suspicious and non-suspicious lesions confirmed or excluded by the Ground Truth as described in the Sections above. BCC: Basal cell carcinoma, SCC: Squamous cell carcinoma, AMN: Atypical melanocytic nevi with uncertain malignant potential.

**Table 5.** Sample size estimates for cutaneous diseases of interest to evaluate the specificity of Sklip System based on the available target population prevalence data.

Sample Size Estimate to Test for Specificity											
Melanoma			BCC			SCC			AMN		
Confirmed	Excluded	Total	Confirmed	Excluded	Total	Confirmed	Excluded	Total	Confirmed	Excluded	Total
2	55	57	11	56	67	32	56	88	4	56	61
0	37	37	1	24	25	2	24	26	0	24	24
2	92	94	12	81	92	33	81	114	4	81	85
2.3%			12.5%			29.2%			5.0%		

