97.4%			95%			95%			95%		
40%			30%			30%			30%		

The sample size was estimated using formulae (1) and (2) to test for sensitivity and specificity, respectively, with  $\alpha = 0.05$  significance level and 10% margin of error for 95% Confidence Interval. The respective sensitivity and specificity values were used to estimate the numbers of suspicious and non-suspicious lesions confirmed or excluded by the Ground Truth as described in the Sections above. BCC: Basal cell carcinoma, SCC: Squamous cell carcinoma, AMN: Atypical melanocytic nevi with uncertain malignant potential.

**Table 6.** Numbers of PSLCs expected to be captured in the estimated sample from the target population.

Lesions	Melanoma Confirmed	Melanoma Excluded	BCC	SCC	AMN	Total non- Melanoma Cancers	Total Malignant Lesions	Total Negative for Malignancy Lesions	Total
Suspicious	9	248	36	84	14	135	144	113	257
Non-Suspicious	0	165	15	36	6	58	58	107	166
Total	10	413	52	121	21	193	203	220	423
Prevalence	2.3%	97.7%	12.5%	29.2%	5.0%	46.7%	49.0%	51.0%	100%
Lesions per Melanoma	1	42	5	13	2	20	21	22	43

A review of all histologically confirmed Melanoma diagnosis made at OHSU within the past 10 years revealed over 3,500 cases. A review of all histologically confirmed non-Melanoma skin cancer diagnosis made at OHSU within the past 5 years revealed over 30,000 cases. Based off these findings, since three (3) additional Satellite Study Sites are each required to contribute at least fifteen (15) percent of the total sample size each, a maximum of 124 Participants at Site #1 OHSU (FDA suggested maximum enrollment cap of 40%) and a minimum of 47 participants (FDA suggested minimum enrollment of 15%) at each additional Site is feasible.

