#### 11.4.2 ANALYSIS OF PRIMARY ENDPOINT(S)

For the Primary Endpoints, the SMSA outputs of “SUSPICIOUS” or “UNREMARKABLE” from Participant-taken DDI will be compared to the Ground Truth, described in the Sections above. For **Melanoma and atypical melanocytic nevi with uncertain malignant potential** (moderate, severe, and high grade atypia; those with pathology reports that include notes such as: borderline, cannot exclude melanoma, cannot exclude early evolving melanoma, unusual features, atypical spitz nevi, suspicion for melanoma, re-excision (or further removal) should be considered or is recommended in the pathologist management comment), a 2x2 table consisting of the following counts (number of PSLCs):

- True Positives (TP): the SMSA output of SUSPICIOUS agrees with the Ground Truth for PSLCs that were

biopsied and were diagnosed as Melanoma or atypical melanocytic nevi with uncertain malignant potential, using Dataset (O) (Histologic diagnosis ground truth (H-GT)),

- False Positives (FP): the SMSA output of SUSPICIOUS does not agree with the benign Ground Truth using Dataset (N) (DDI dermoscopic diagnosis ground truth) and Dataset (O)
- False Negatives (FN): the SMSA output of UNREMARKABLE does not agree with the Ground Truth for PSLCs that were biopsied and diagnosed as Melanoma or atypical melanocytic nevi with uncertain malignant potential using Dataset (O)
- True Negatives (TN): the SMSA output of UNREMARKABLE agrees with the benign Ground Truth, using both Dataset (N) and Dataset (O)

For **Melanoma and atypical melanocytic nevi with uncertain malignant potential**, Sensitivity ( $TP \div (TP + FN)$ ) of the Sklip System will be calculated with a lower one-sided 95% confidence interval using the Exact (Clopper-Pearson) method. For **Squamous cell carcinoma** and for **Basal cell carcinoma**, Sensitivity and lower one-sided confidence intervals will be estimated in the same manner as for Melanoma and atypical melanocytic nevi with uncertain malignant potential.

Specificity ( $TN \div (FP + TN)$ ) will be the same for Melanoma and atypical melanocytic nevi with uncertain malignant potential, SCC, and BCC, where:

- False Positives (FP): the SMSA output of SUSPICIOUS does not agree with the benign Ground Truth, using Dataset (N) and Dataset (O)
- True Negatives (TN): the SMSA output of UNREMARKABLE agrees with the benign Ground Truth, using Dataset (N) and Dataset (O)

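### The 423-lesion size rests on a 97.4% sensitivity for melanoma alone that the protocol elsewhere gives for melanoma and atypical nevi together, and no planned analysis reports sensitivity for all melanomas

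*Combined protocol and SAP*

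**What the plan says.** **Sizing.** Section 11.2 uses formula (1) with a 10% margin of error. Table 4 has separate columns for melanoma (prevalence 2.3%, sensitivity 97.4%) and atypical melanocytic nevi (5.0%, 95%). The melanoma column gives the largest number, 423, described as "based on SMSA performance of sensitivity for melanoma of 97.4" per cent. The prevalences for melanoma, squamous cell and basal cell carcinoma come from site biopsy records that "averaged 2.3%, 12.5% and 29.2% of in-person dermatology Provider visits". That sentence does not cover atypical nevi, and no source is given for their 5.0%.

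**The same 97.4% elsewhere.** The Synopsis entry on the algorithm gives "97.4% for melanoma and atypical melanocytic nevi with uncertain malignant potential". Section 1.1 also attaches the figure to both diagnoses. Section 1.2 reports "sensitivity for melanoma and atypical melanocytic nevi with uncertain malignant potential is 97.4% (2023", and the Device Description in section 6.1.1 does the same: "Melanoma and atypical melanocytic nevi with uncertain malignant potential sensitivity Performance of 97.4% (2023".

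**Endpoint.** Sections 2.1 and 11.1 set the 95% sensitivity goal for the pooled class. Section 11.4.2 counts as true positives the flagged lesions that were "biopsied and were diagnosed as Melanoma or atypical melanocytic nevi with uncertain malignant potential, using Dataset (O". It prescribes a lower one-sided 95% Clopper-Pearson limit, but the documents do not say whether the goal applies to the estimate or to that limit.

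**Melanoma by itself.** Exploratory endpoints 1 and 2 list the pooled class, squamous cell carcinoma and basal cell carcinoma. Exploratory endpoint 3 takes only melanomas under 0.8 mm Breslow depth. Exploratory endpoint 4 counts lesions. The subgroups in section 11.4.6 are skin type and possibly site.

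**The concern.** There are two problems, and they are separate.

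The first is the input. The row that sets the trial's size combines a sensitivity that most of the protocol assigns to the pooled class with a prevalence for melanoma only. The quantity being sized, sensitivity for melanoma, is not one that section 11.4.2 estimates. The stated justification therefore does not describe the primary endpoint.

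The second is the endpoint. Atypical nevi are expected to supply about two thirds of the pooled positives, so the pooled figure mostly reflects them. A reader who wants to know how often a stand-alone triage tool misses melanoma would find no planned estimate, although the trial was sized on exactly that.

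**Working it through.** **Inputs.** From section 11.2 and Tables 4 and 6: Z = 1.96, d = 0.10; prevalence 2.3% (melanoma) and 5.0% (atypical nevi); sensitivity 97.4% and 95%; 1.5 lesions per participant; 10% drop-out. Table 6 expects 10 melanomas and 21 atypical nevi among 423 lesions.

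**Reproducing the plan.** Formula (1) is n = Z² × Se × (1 − Se) / (d² × Prev).

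- Melanoma: 1.96² × 0.974 × 0.026 / (0.01 × 0.023) = 422.98, so 423.
- Participants: 423 / 1.5 × 1.10 = 310.2, stated as 310.
- Atypical nevi: 1.96² × 0.95 × 0.05 / (0.01 × 0.05) = 364.95, stated as 365.

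All three agree with the protocol.

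**If 97.4% is the pooled figure.** Pooled prevalence is 2.3% + 5.0% = 7.3%. Then n = 1.96² × 0.974 × 0.026 / (0.01 × 0.073) = 133.3, so 134 lesions.

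**Melanoma alone.** If 97.4% is pooled, the documents give no melanoma-only sensitivity. Over an assumed range, formula (1) at 2.3% prevalence gives:

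| Assumed melanoma sensitivity | Lesions |
|---|---|
| 99% | 166 |
| 97.4% | 423 |
| 95% (value in the other columns of Table 4) | 794 |
| 90% | 1,504 |

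**What 423 lesions delivers.** Expected melanomas are 423 × 0.023 = 9.7 and expected atypical nevi 423 × 0.05 = 21.2, about 31 pooled positives. Exact (Clopper-Pearson) results:

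| Result | Estimate | Two-sided 95% CI | Lower one-sided 95% limit |
|---|---|---|---|
| 31/31 pooled | 100% | from 88.8% | 90.8% |
| 30/31 pooled | 96.8% | 83.3% to 99.9% | 85.6% |
| 29/31 pooled | 93.5% | from 78.6% | 81.1% |
| 9/10 melanoma | 90% | 55.5% to 99.7% | 60.6% |

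**How much pooling can hide, with the goal read on the point estimate.** One miss passes (96.8%) and two fail (93.5%). If the one miss is a melanoma, melanoma is 9/10, the lowest observed melanoma result that passes at the expected counts.

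For true rates in the 10:21 mix, melanoma sensitivity at pooled 95% is (0.95 × 31 − 21 × s) / 10, where s is sensitivity for atypical nevi:

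- s = 100%: (29.45 − 21) / 10 = 84.5%
- s = 97.4%: (29.45 − 20.454) / 10 = 90.0%
- s = 95%: (29.45 − 19.95) / 10 = 95.0%

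**Goal read on the lower one-sided limit.** Even 31/31 fails: 0.05^(1/31) = 90.8%. With no misses, 59 positives would be needed, since 0.05^(1/59) is the first such value to reach 95%. At the expected counts nothing passes, so no missed melanoma can be hidden behind a pass.

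**The case against.** Pooling is a declared choice. The protocol's target is lesions that need biopsy, the class is defined the same way throughout, and the goals are said to have been reviewed with the FDA. No passage draws a melanoma-only claim from the pooled result. At the protocol's own margin, 423 exceeds the 134 that the pooled class needs, so for the primary endpoint the mismatch errs on the safe side. Section 11.2 also says the sizing used performance data for melanoma, so the sponsor may hold a melanoma-only 97.4%. All of this stands, and it limits the point. It does not settle which label is right: if section 11.2 is correct, the other four places are mislabelled.

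A reader might infer more, and the documents do not support it:

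- **That the inputs are arithmetically impossible.** Weighting by this trial's prevalences, a pooled 97.4% with nevi at 95% would imply melanoma sensitivity of (7.3 × 0.974 − 5.0 × 0.95) / 2.3 = 102.6%. But a reported sensitivity reflects the case mix of the study behind it, which is not given. Melanoma stays at or below 100% if melanomas were at least (97.4 − 95) / (100 − 95) = 48% of that study's pooled positives. The 95% also looks like a uniform planning value: Table 4 uses it for basal and squamous cell carcinoma too, where the Synopsis reports 97.3% and 97.0%.
- **That the goal can simply be met with melanoma sensitivity near 85%.** This is a limiting case for the true rate. It needs every atypical nevus flagged and the goal read on the point estimate.
- **That the label causes the masking.** It does not. Pooling would have the same effect if the 97.4% were labelled correctly.

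**Conclusion.** The point holds in two parts.

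1. The documents conflict on which class 97.4% describes, and the size-setting calculation does not describe the primary endpoint. This does not make 423 too small for the pooled class at a 10% margin (134 would do). It leaves the melanoma-only size without a supported input: 423 at 97.4%, 794 at 95%.
2. No planned analysis estimates sensitivity for all melanomas, and about 21 of the 31 expected pooled positives are atypical nevi. On the point-estimate reading, a pass at 30/31 is compatible with 9/10 melanomas. The true melanoma sensitivity compatible with a pooled 95% runs from 84.5% to 95.0% as sensitivity for atypical nevi runs from 100% to 95%. On the lower-limit reading no result at the expected counts passes, and the masking question does not arise.

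The counts rest on Table 6 and on the unsourced 5.0%. The conclusion that 97.4% is probably pooled rests on four places against one, not on sight of the performance study.

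**What to change.** **Section 11.2.** State which class the 97.4% describes and bring the Synopsis and sections 1.1, 1.2, 6.1.1 and 11.2 into agreement. Add a row for the pooled class at 7.3% prevalence and give the source of the 5.0%. Restate what 423 lesions delivers, using the exact intervals of the planned analysis: about 31 pooled positives (for example 30/31, 95% CI 83.3% to 99.9%) and about 10 melanomas (9/10, 55.5% to 99.7%). A normal-approximation half-width would be misleading with so few expected misses.

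**Section 11.4.2.** Prespecify sensitivity with exact intervals for all melanomas and for atypical nevi separately, beside the pooled figure, and state that no melanoma-specific claim rests on the pooled figure. The histologic ground truth (Dataset O) already provides the diagnoses needed for the split.

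**Cost.** Wording and a few table rows, with no extra enrolment or procedures. The downside is a visibly wide melanoma-only interval.

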## 5.5 PARTICIPANT DISCONTINUATION OR WITHDRAWAL

Participants are free to withdraw consent and discontinue participation in the Study at any time and without prejudice to further treatment. If a Participant withdraws consent, they should be asked to specify if they are withdrawing consent to all further participation in the Study or if they are choosing to withdraw only from further Study intervention, meaning that further follow-up and data collection about their disease and health status is allowable. The Participant should also be asked about their consent to the future use of their Study-generated data and any biological samples, as applicable.

No further Participant contact will be made if the Participant withdraws consent for participation in the Study. Information about the reason(s) for discontinuation will be collected at the time the Participant withdraws consent.

A Participant may also be withdrawn from the Study by the Investigator, local IRB, or regulatory authorities.

Reasons for a Participant to discontinue the Study may include the following:

- Participant dies or is lost to follow-up
- Participant withdraws consent for any further participation
- The end of Study is reached
- Significant Study intervention non-compliance
- If any clinical adverse event (AE), laboratory abnormality, or other medical condition or situation occurs such that continued participation in the Study would not be in the best interest of the Participant
- If the Participant meets an exclusion criterion (either newly developed or not previously recognized) that precludes further Study participation

In the event of a pregnancy, the Study intervention will be immediately reported to the appropriate committees and their participation in the Study will be discontinued. Refer to Section 10.6.6 regarding reporting of pregnancy

In the event a Participant withdraws early from the Study, Investigator(s) will attempt to find a replacement to enroll in the Study to meet target number of Participants.

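### Section 11.2 allows for 10% drop-out by multiplying by 1.10 instead of dividing by 0.90, so before any replacement 310 participants are expected to yield about 418 lesions, not 423

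*Combined protocol and SAP*

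**What the plan says.** Section 11.2 sizes the study on the precision of melanoma sensitivity. The inputs to formula (1) are:

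- a "significance level and 10% margin of error for 95% Confidence Interval";
- a sensitivity "based on SMSA performance of sensitivity for melanoma of 97.4" percent;
- a melanoma prevalence of 2.3%, from historical biopsy results that "averaged 2.3%, 12.5% and 29.2% of in-person dermatology Provider visits".

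The section concludes that "the size estimate calculated using the sensitivity value for detecting melanoma (423 cases [lesions]) yields the largest number". It then converts lesions to participants: "we expect a case submission rate of 1.5 per Study Participant". Drop-out is added last: "Assuming a 10% drop-out rate a total number of 310 Participants (dropout-inflated sample size) will be needed", with the arithmetic printed as "310 = 423 ÷ 1.5 × 1.10". Table 6 shows a total of 423 lesions as the number expected to be captured.

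Replacement is dealt with elsewhere. Section 5.5 says that for early withdrawals "Investigator(s) will attempt to find a replacement to enroll in the Study to meet target number of Participants". Section 5.5.1 permits replacement of those who withdraw before or after receiving the intervention. Neither provision enters the calculation of 310.

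**The concern.** A 10% drop-out rate means that 10% of the people enrolled are lost. To finish with a given number of contributors, that number is divided by 0.90. Multiplying by 1.10 adds 10% of the contributors, which is a smaller allowance. The plan calls 310 a drop-out-inflated figure, so it should reach 423 lesions under the plan's own drop-out and submission rates.

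What is at stake is the consistency of a stated sample size in a trial that Section 11.1 calls pivotal. Three statements in Section 11.2 cannot all hold without replacement: 310 enrolled, 10% drop-out, and 423 lesions captured. The 310 also appears in the Synopsis, in the projected accrual table of Section 4.4.1 and in the device count of Section 6.1.2, and it underlies the site limits of 124 and 47 in Section 11.2. Its derivation should therefore be right even though the numerical effect is small.

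**Working it through.** **Inputs, all from Section 11.2:** z = 1.96; d = 0.10; sensitivity 0.974; melanoma prevalence 0.023; 1.5 lesions per participant; 10% drop-out.

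**1. Reproduce the plan's figures.**
- Lesions, formula (1): 1.96² × 0.974 × 0.026 ÷ (0.10² × 0.023) = 422.98, so 423. This agrees with the plan.
- Participants contributing lesions: 423 ÷ 1.5 = 282.
- Inflation as printed: 282 × 1.10 = 310.2, stated as 310. This agrees with the plan.

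Rounding therefore accounts for only 0.2 of a participant.

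**2. Inflate for loss of 10% of those enrolled.**
- 282 ÷ 0.90 = 313.3, so 314, which is 4 participants (1.3%) more than 310.
- Check: 314 × 0.90 × 1.5 = 423.9, which meets 423.

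**3. Run the plan's 310 forward, without replacement.**
- Participants remaining: 310 × 0.90 = 279.
- Expected submitted lesions: 279 × 1.5 = 418.5.
- Shortfall: 423 − 418.5 = 4.5 lesions, and 4.5 ÷ 423 = 1.1%.

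For 310 to yield 423 lesions, drop-out could be at most 1 − 282 ÷ 310 = 9.03%, or the submission rate would have to be at least 423 ÷ 279 = 1.516.

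**4. Effect on the quantity used for sizing (melanoma alone, normal approximation).**

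| | 423 lesions | 418.5 lesions |
|---|---|---|
| Expected melanomas (× 0.023) | 9.73 | 9.63 |
| Margin, 1.96 × √(0.974 × 0.026 ÷ melanomas) | 10.00% | 10.05% |

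**5. Effect on the combined primary endpoint (melanoma and atypical nevi).** Table 6 expects 10 + 21 = 31 such lesions. Adding its two prevalences, 2.3% + 5.0% = 7.3%, gives 423 × 0.073 = 30.9 and 418.5 × 0.073 = 30.6. With 30.6 lesions the normal-approximation margin is about 5.6% at 97.4% sensitivity and about 7.7% at 95%. Both are inside the 10% target.

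**6. Scale against the other inputs.**
- Section 11.2 cites 1.02 to 1.9 images per participant from earlier studies. Over that range 279 participants give 279 × 1.02 = 285 to 279 × 1.9 = 530 lesions.
- A prevalence printed as 2.3% could be anything from 2.25% to 2.35%. Formula (1) then gives about 432 down to 414 lesions, a band that contains 418.5.

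**The case against.** The arithmetic is not in dispute; the case against the point is about materiality and context.

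- **Size.** The 4.5-lesion gap is smaller than the uncertainty from rounding the prevalence and far smaller than that from the submission rate. This stands, and it is why the point is minor. It does not make the printed formula correct.
- **Replacement.** Section 5.2 enrols until the target number is met, and Sections 5.5 and 5.5.1 provide for replacing withdrawals. Only 282 − 279 = 3 further contributors are needed, against 31 expected drop-outs, so the gap may well close in practice. A reader might infer that 310 participants cannot deliver 423 lesions; the documents do not support that. But replacement is attempted or permitted, not guaranteed, and it is not part of the 310. The statement holds for the calculation as written, before replacement.
- **Drop-outs may still contribute lesions.** Section 5.6 defines loss to follow-up by a missing survey, Section 11.3 analyses everyone enrolled regardless of adherence, and Section 11.5 uses all available data. Some participants counted as lost could therefore have supplied usable images. That is fair as to conduct. However, inflating for drop-out at all presumes that drop-outs supply no lesions, so the plan's own calculation implies this reading.
- **Wrong group.** The primary endpoint combines melanoma with atypical nevi, and Section 11.4.2 reports Clopper-Pearson intervals. A reader might infer that this endpoint misses its precision target because of the error. It does not: step 5 shows that it is barely affected. The 10.05% is a melanoma-only planning figure, quoted because that is the basis on which Section 11.2 chose 423.

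**Conclusion.** The point holds as a minor arithmetic correction. The inflation formula in Section 11.2 is wrong. Under the plan's own inputs, 310 enrolled are expected to yield about 418 submitted lesions instead of 423, and the inflation that meets the target is 314. The consequence is about 1% fewer lesions, 0.1 fewer expected melanomas, and 0.05 percentage points on the melanoma-only planning margin. It does not threaten the design or the interpretation of any endpoint.

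The result assumes 10% loss among those enrolled, 1.5 lesions from each remaining participant, none from drop-outs, and no replacement.

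The 418 should not be read as a count of evaluable lesions. Section 11.4.1 excludes lesions with three ERROR outputs and Section 11.2 makes no allowance for them, so the number analysed could be lower by an amount that the documents do not let one estimate.

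**What to change.** Keep 310 and make these text changes in Section 11.2:

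1. Correct the printed formula. Show that a 10% loss would call for 423 ÷ 1.5 ÷ 0.90 = 314, and that the planned 310 gives 310 × 0.90 × 1.5 = about 418 expected lesions.
2. Describe the 418 as lesions submitted after 10% drop-out, without replacement and before exclusion of lesions with three ERROR outputs. Give the matching melanoma-only planning margin of about 10.05%.
3. Bring Table 6 into line, since its total of 423 is presented as the number expected to be captured. Restate the total as about 418 on the same basis and rescale the counts.

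The cost is a few lines of text and one table, with no added enrolment and no change to the site limits. If the sponsor prefers to adopt 314, the 310 must also change in the Synopsis, Section 4.4.1 and Section 6.1.2. The site limits would need recalculating (40% × 314 = 125.6; 15% × 314 = 47.1). The size of the effect does not require this.
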